5.4.2.3 Secondary Endpoints (Efficacy)

Time to event and duration efficacy secondary endpoints include:

- **Time to alleviation or improvement of COVID-19 symptoms (Items 1–12 of the COVID-19 Symptom Diary) maintained for a duration of 21.5 hours**
 - Time to alleviation or improvement is defined as the length of time (hours) taken from start of treatment to the point at which all of the following three criteria are met and maintained for a concurrent duration of at least 21.5 hours:
 - Alleviation of all new COVID-19 symptoms, defined as a score of 0 [none] or 1 [mild] of the COVID-19 Symptom Diary
 - Improvement of all pre-existing symptoms that had worsened due to COVID-19, defined as at least a single category improvement from baseline on the Likert scale. For example, a symptom classed as severe at baseline must improve to moderate, mild, or none, and a symptom classed as moderate at baseline must improve to mild or none.
 - Maintain/improvement of all pre-existing symptoms that had not worsened due to COVID-19, defined as either remaining the same score or at least a single category improvement from baseline on the Likert scale.
- **Time to alleviation or improvement of COVID-19 symptoms (Items 1–12 of the COVID-19 Symptom Diary) maintained for a duration of 43 hours**
 - Time to alleviation or improvement is defined as the length of time (hours) taken from start of treatment to the point at which all of the following three criteria are met and maintained for a concurrent duration of at least 43 hours:
 - Alleviation of all new COVID-19 symptoms, defined as a score of 0 [none] or 1 [mild] of the COVID-19 Symptom Diary
 - Improvement of all pre-existing symptoms that had worsened due to COVID-19, defined as at least a single category improvement from baseline on the Likert scale. For example, a symptom classed as severe at baseline must improve to moderate, mild, or none, and a symptom classed as moderate at baseline must improve to mild or none.
 - Maintain/improvement of all pre-existing symptoms that had not worsened due to COVID-19, defined as either remaining the same score or at least a single category improvement from baseline on the Likert scale.

The efficacy endpoint definition includes both alleviation of new COVID-19 symptoms and maintenance/improvement of pre-existing COVID-19 symptoms to allow for the possibility that some patients may have underlying health conditions with symptoms similar to those observed with COVID-19 (e.g., cough in a patient with chronic obstructive pulmonary disease). At screening, patients will be assessed with a 14-item COVID-19 symptom severity assessment to identify pre-existing symptoms (within the prior 30 days), and assess if they worsened due to COVID-19. Symptoms that are not pre-existing are considered to be new symptoms and need to achieve sustained alleviation (score of 0 or 1) to meet the endpoint, as described above.

- **Time to alleviation of COVID-19 signs and symptoms maintained for a duration of 21.5 hours**
 - Time to alleviation of COVID-19 symptoms is defined as the length of time (hours) taken from start of treatment to the point at which the following criterion is met and maintained for at least 21.5 hours: Score of 0 or 1 on Items 1–12 of the COVID-19 Symptom Diary, regardless of if the symptom is pre-existing or new.
- **Time to alleviation of COVID-19 signs and symptoms maintained for a duration of 43 hours**
 - Time to alleviation of COVID-19 symptoms is defined as the length of time (hours) taken from start of treatment to the point at which the following criterion is met and maintained for at least 43 hours: Score of 0 or 1 on Items 1–12 of the COVID-19 Symptom Diary, regardless of if the symptom is pre-existing or new.
- **Duration of fever**
 - Duration of fever is defined as the time from start of treatment to return to an afebrile state (temperature $\leq 37.5^{\circ}\text{C}$) maintained for at least 21.5 hours.
- **Time to alleviation of an individual symptom**
 - Time to alleviation of an individual symptom is defined as the length of time (hours) taken from the start of treatment to the point at which the following criterion is met and maintained (for each individual symptom) for at least 21.5 hours:
 - Score of 0 or 1 for Items 1–12 of the COVID-19 Symptom Diary
 - Score of 0 for Items 13 and 14 of the COVID-19 Symptom Diary

For each of these endpoints, the time at which the endpoint is met is the time of the start of the period when the criterion is met.

These endpoints will be summarized using descriptive statistics by treatment group, as well as Kaplan-Meier plots where appropriate. The median time to response will be presented along with the 80% CI. For all cohorts, the efficacy time to event endpoints will be described through Day 28 between the AT-527 group and the combined placebo group from all available cohorts using the mITTi population.

A summary of the symptom severity for each symptom in the COVID-19 symptom diary will be provided at baseline, Day 14 and Day 28 for each treatment group and pooled placebo group. Day 14 (morning) assessments are to be used for the Day 14 summary. If the morning sample is missing, the evening sample will be used.

For efficacy time to event endpoints, deaths will be right censored at Day 28. Consequently, for these endpoints, participants censored on Day 28 reflect two different states, death and failure to meet the improvement outcome criterion. Therefore, it is

important to understand the outcome in the context of the number and timing of deaths by treatment group.

Intercurrent events are those that occur after treatment initiation and either preclude observation of the variable or affect its interpretation. Intercurrent events and missing data will be accounted for through censoring rules, as described in [Table 9](#) below.

Table 9 Efficacy Time to Event Censoring

Event	Censor	Date and Time
Death prior to meeting endpoint	Yes	Final timepoint on Day 28
Discontinuation or lost to follow-up up to Day 28 for any reason prior to meeting endpoint	Yes	Last observed COVID-19 symptom diary assessment
Do not meet the endpoint	Yes	Final timepoint on Day 28

Frequency efficacy endpoints include:

- **Frequency of COVID-19-related complications**
 - COVID-19-related complications include: death, hospitalization, radiologically confirmed pneumonia, acute respiratory failure, sepsis, coagulopathy, pericarditis, myocarditis, and cardiac failure.

For frequency efficacy endpoints, the number, proportion and difference in proportions between the AT-527 group and the pooled placebo group from all available cohorts, along with 80% CIs will be presented by treatment group.

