3.3.5 Rationale for Non-Standard Clinical Outcome Assessments

At the onset of the COVID-19 pandemic, there was limited understanding of what constituted disease progression in COVID-19 and how the symptoms were manifested and impacted patients' lives. Given the heterogeneous nature of COVID-19–related symptoms in outpatients, key COVID-19–related symptoms should be assessed systematically to provide an accurate evaluation. Currently, there are no validated patient-reported outcome (PRO) tools for the assessment of COVID-19 symptoms. This study will utilize a PRO instrument based on the example U.S. Food and Drug Administration (FDA) COVID-19 PRO instrument that assesses 14 of the most common COVID-19 symptoms (FDA 2020). The symptom items used in this PRO are derived from information provided by the Centers for Disease Control and Prevention (CDC) as of 28 August 2020.

4. **MATERIALS AND METHODS**

4.1 **PATIENTS**

Up to approximately 404 non-hospitalized adult patients with mild or moderate COVID-19 will be enrolled in this study.

4.1.1 **Inclusion Criteria**

Patients must meet the following criteria for study entry:

- Signed Informed Consent Form
- Age ≥ 18 years at time of signing Informed Consent Form
- Willing and able to comply with the study protocol and all study procedures, in the opinion of the investigator
- Positive SARS-CoV-2 diagnostic test (RT-PCR or rapid antigen test) at screening
- Has symptoms consistent with mild or moderate COVID-19, as determined by the investigator, with onset ≤ 5 days prior to randomization
- For women of childbearing potential: agreement to remain abstinent (refrain from heterosexual intercourse) or use adequate contraception during the treatment period and for 30 days after the final dose of study drug.

A woman is considered to be of childbearing potential if she is postmenarchal, has not reached a postmenopausal state (≥ 12 continuous months of amenorrhea with no identified cause other than menopause), and is not permanently infertile due to surgery (i.e., removal of ovaries, fallopian tubes, and/or uterus) or another cause as determined by the investigator (e.g., Müllerian agenesis). The definition of childbearing potential may be adapted for alignment with local guidelines or regulations. Women of childbearing potential must be established on their chosen method of contraception at screening.

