Appendix 1: Schedule of Activities for Cohort A

COVID-19=coronavirus disease 2019; ET=early termination; PK=pharmacokinetic; RT-PCR=reverse-transcription polymerase chain reaction; SARS-CoV-2=severe acute respiratory syndrome coronavirus-2; PRO=patient-reported outcome; UV=unscheduled visit.

Notes: On treatment days (Days 1–5), all assessments should be performed prior to dosing, unless otherwise specified.

- ^a Screening assessments may be performed up to 72 hours prior to Day 1 or on Day 1.
- ^b An unscheduled visit represents a visit that is not specified by the protocol but is determined to be necessary by the investigator or Sponsor (e.g., for evaluation of an adverse event). Assessments (including PK sample collection) should be performed as clinically indicated. For unscheduled visits occurring after Day 7, PK sample collection is not required.
- ^c Patients who discontinue study drug prematurely will continue to complete assessments as indicated until the end of the study. Patients who discontinue from study participation will have an early termination visit 7 (± 2) days after their final dose of study drug. Patients who discontinue from the study after Day 14 will not be required to complete an early termination visit.
- ^d Required follow-up information will be collected via telephone call at Day 14 (± 2 days) and Day 33 (± 3 days).
- ^e Informed consent must be documented before any study-specific screening procedure is performed.
- ^f For patients at participating sites who have provided written or electronic informed consent to participate in mobile nursing visits, this assessment or procedure may be performed by a trained nursing professional at the patient's home.
- ^g COVID-19 Symptom Diary includes questions regarding symptoms (Items 1–14) and the Patient Global Impression of Severity. On assessment visit days, questionnaires will be self-administered before the patient receives any information on disease status, prior to the performance of non-PRO assessments, and prior to the administration of study treatment. On Day 1, the first diary questionnaire should be completed prior to the first dose. On Days 1–14, the questionnaire (including recording of temperature) should be completed twice a day (morning and evening) at the same time each day.
- ^h On Days 15–28, the questionnaire (including recording of temperature) should be completed once a day in the evening at the same time each day.

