5. STATISTICAL ANALYSES

5.1 GENERAL CONSIDERATION

All virology and efficacy analyses will be performed on the mITTi population.

All primary and secondary virology endpoints will be produced using the nasopharyngeal swab samples. Additional descriptive analyses for saliva and serum samples will be performed on an exploratory basis for the primary and secondary virology endpoints, as required. A summary of the sampling differences between cohorts is provided in [Table 3](#). Refer to Appendix 1 and Appendix 2 of the study protocol for further details.

No alpha adjustments for multiple comparisons are planned.

For all cohorts, the primary virology analysis will be performed as part of a Day 10 Review (accompanied with key safety review if deemed necessary, see [Section 5.7.1](#)) which is to be completed after all patients enrolled in the current cohort have completed assessments through Day 10. Other endpoints will be analyzed at the completion of each full cohort or at the completion of the study. All analyses at the Day 10 review or at the completion of each cohort will compare each AT-527 dose group and a combined placebo group, including all placebo patients enrolled across cohorts up to the cohort being analyzed, while analyses performed at the completion of the study will compare each AT-527 dose group and a combined placebo group from all cohorts.

Table 3 Differences in Virology Sampling Between Cohorts

Assessment	Cohort A	Cohorts B–E
Nasopharyngeal swab sample for COVID-19 virology	Once a day on Days 1, 3, 5, and 7	Once a day on Days 1, 3, 5, and 7
Saliva sample for COVID-19 virology	NA	Once a day on Days 1, 3, 5, and 7
Serum sample for anti-SARS-CoV-2 antibodies and viral RNA	Once a day on Days 1 and 7	Once a day on Days 1, 3, 5, and 7

COVID-19 = coronavirus disease 2019; NA = not applicable; SARS-CoV-2 = severe acute respiratory syndrome coronavirus-2.

For virology endpoints, the time windows for each assessment are given in [Table 4](#). The time windows will be used for all virology endpoints except the time-to-event endpoints.

Table 4 Virology Assessment Time Windows

Scheduled Timepoint ^{a, b, d}	Acceptable Time Window
Baseline (Day 1 pre-dose)	Day 1 pre-dose ^c
Day 3	Day 2 – Day 3
Day 5	Day 4 – Day 5
Day 7	Day 6 – Day 8

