5.4 SECONDARY ENDPOINTS ANALYSES

All secondary endpoints will be analyzed descriptively and summary statistics will be presented. Descriptive comparisons will be made for each AT-527 group and a pooled placebo group containing patients from all cohorts. For time to event endpoints, a Kaplan-Meier plot and the median time to response will be presented along with the 80% CI. For proportion, frequency and incidence endpoints, the number, proportion and difference in proportions along with 80% CIs will be presented. For area under the curve (AUC) endpoints, summary statistics will be presented.

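### Patients whose diary items are all none or mild before dosing can count as recovered at time zero in the symptom endpoints, and the SAP has no rule for them

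*SAP*

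**What the plan says.** **Entry.** Protocol 4.1.1 requires that the patient "Has symptoms consistent with mild or moderate COVID-19, as determined by the investigator, with onset ≤ 5 days prior to randomization". No criterion asks for any diary item to be moderate or severe.

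**Time to alleviation (21.5 h and 43 h).** SAP 5.4.2.3 defines response as "Score of 0 or 1 on Items 1–12 of the COVID-19 Symptom Diary, regardless of if the symptom is pre-existing or new".

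**Time to alleviation or improvement (21.5 h and 43 h).** The same section applies three criteria together:
- each new symptom must be rated none or mild;
- for symptoms the patient had before and that the illness made worse, the rule is "Improvement of all pre-existing symptoms that had worsened due to COVID-19, defined as at least a single category improvement from baseline on the Likert scale";
- pre-existing symptoms that COVID-19 had not worsened must be no worse than at baseline.

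**Timing.** For these endpoints "the time at which the endpoint is met is the time of the start of the period when the criterion is met". Footnote g of Protocol Appendix 1, repeated in Appendices 2 and 3, says: "On Day 1, the first diary questionnaire should be completed prior to the first dose".

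**Population and role.** SAP 5.1 states: "All virology and efficacy analyses will be performed on the mITTi population". Membership of mITTi depends on randomization, dosing and a quantifiable PCR result, not on symptoms. SAP Table 9 covers death, discontinuation and never meeting the endpoint. It does not cover a criterion already met at baseline. SAP 5.4 states: "All secondary endpoints will be analyzed descriptively and summary statistics will be presented". Tests (generalized Wilcoxon or log-rank) are optional under SAP 5.4.1.

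**The concern.** The response level of the alleviation endpoints is a level at which a patient may enter the trial. Someone with, say, mild cough, fatigue and headache on the pre-dose diary has COVID-19 symptoms but already meets the criterion. If no item rises above mild during the maintenance period, the event is dated to the pre-dose entry.

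Such events carry no information about treatment. They pull both Kaplan-Meier medians towards zero and shrink the difference between them, and the median is the planned summary. Chance differences between arms in the number of such patients add noise to any test. The SAP also does not say whether the event time is zero or slightly negative, so a programmer would have to decide. Protocol 6.1 gives better characterization of the secondary endpoints as one benefit of the larger Cohort E, so the gap is worth closing.

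**Working it through.** **1. The plan's own figures.** The documents state no sample size, event count or power for any symptom endpoint. Only viral RNA is sized. For Cohort E (Protocol 6.1: difference 0.5 log10, SD 1.25, one-sided 2.5%, 80% power), n = 2(1.960 + 0.842)² × (1.25/0.5)² = 98.1, so 99 per arm. The exact t-test at the stated 100 gives 80.4% power, and 100/0.9 rounds up to 112. That sizing reproduces. It is used below only as the source of 100 per arm.

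**2. Who is an event at time zero?** Each rule is applied to the pre-dose diary, assuming the state is then maintained.

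| Endpoint | Already met before dosing when |
|---|---|
| Time to alleviation, 21.5 h and 43 h | Items 1–12 are all 0 or 1 |
| Alleviation or improvement, 21.5 h and 43 h | every new symptom is 0 or 1 and there is no pre-existing symptom worsened by COVID-19 |
| Duration of fever | temperature is 37.5°C or lower |
| Individual symptom | that item is 0 or 1 (Items 1–12) or 0 (Items 13–14) |

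In the second row, a worsened pre-existing symptom that is mild at baseline must still become none. An unworsened one may stay at any severity.

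**3. Effect on the medians.** Inputs assumed, not in the documents: a share f of each arm has its event at time zero, and the others recover exponentially with median M = 240 h (placebo) or 180 h (active).

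S(t) = (1 − f) × exp(−t ln 2 / M). Setting S(t) = 0.5 gives median = M × [1 + log2(1 − f)] for f below 50%, and zero otherwise.

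| f | 1 + log2(1 − f) | Placebo (h) | Active (h) | Difference (h) |
|---|---|---|---|---|
| 0 | 1.000 | 240 | 180 | 60 |
| 10% | 0.848 | 203.5 | 152.6 | 51 |
| 20% | 0.678 | 162.7 | 122.1 | 41 |
| 30% | 0.485 | 116.5 | 87.4 | 29 |
| 40% | 0.263 | 63.1 | 47.3 | 16 |
| 50% | 0 | 0 | 0 | 0 |

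The ratio of medians stays at 4/3 until both reach zero. The difference does not. For an individual symptom, both medians are zero once half or more of each arm is already at threshold for that item and stays there.

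**4. Effect on the optional tests.** Simulated power with the same medians, 100 per arm, a 12-hourly diary and a Day 28 cut-off:

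| f, one-sided alpha | Wilcoxon, all mITTi | Wilcoxon, restricted | Log-rank, all mITTi | Log-rank, restricted |
|---|---|---|---|---|
| 20%, 2.5% | 19% | 33% | 33% | 39% |
| 40%, 2.5% | 9% | 26% | 21% | 29% |
| 20%, 10% | 45% | 62% | 61% | 67% |

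Repeat simulations moved single figures by up to 5 points but did not change the ordering. Wilcoxon loses more because it weights each event time by the number at risk, which is largest at time zero.

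A larger effect gives the same pattern. With hazard ratio 1.5, placebo median 10 days and one-sided 2.5%, simulated log-rank power on all patients is 77, 59 and 38% at f = 0, 20 and 40%, and Wilcoxon 67, 36 and 14%. After restriction, Schoenfeld's formula for log-rank gives Φ(√(144/4) × ln 1.5 − 1.96) = 68% at f = 20% (144 events) and Φ(√(108/4) × ln 1.5 − 1.96) = 56% at f = 40% (108 events). Restriction gains power despite the smaller number of patients.

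**The case against.** **Mild disease is not a mild diary.** The entry term is an investigator's disease category. The diary scores each item at its worst. Entry permits an all-mild diary but says nothing about how common it is. This stands: f is unknown, and at f = 10% the median difference falls only from 60 to 51 h.

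**The maintenance rule removes some of these patients.** Patients enter within 5 days of onset, and an all-mild patient with any item reaching moderate within 21.5 or 43 h is not a time-zero event. This also stands. f is at most the all-mild share, and is no larger at 43 h than at 21.5 h.

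**Not all four composite endpoints behave alike.** A reader might infer that any all-mild patient meets all four at baseline. SAP 5.4.2.3 does not support that, because a worsened pre-existing symptom must improve by a category.

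**The endpoints are descriptive.** They are unpowered, tests are optional, and log-rank is offered equally with Wilcoxon. The 2.5% level and 100 per arm come from the protocol's Cohort E sizing for viral RNA. The SAP uses one-sided 10% for its primary analysis and 80% intervals, and there the log-rank loss at f = 20% is modest (61% against 67%). SAP 5.4.1 allows stratified tests, and stratifying on pre-dose response status would take the time-zero block out of the test. No such covariate is named, however, and stratification would not repair the medians.

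**The problem would be partly visible.** Baseline severity is summarized (SAP 5.4.2.3 and 5.7.3), and Kaplan-Meier curves would drop at zero. Measuring from the start of treatment can be read as giving zero rather than a negative time, and the fever definition implies that the patient starts febrile. None of this restricts an analysis set or states a rule.

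**Conclusion.** The gap is in the text. For the two time-to-alleviation endpoints, a patient at none or mild on every item before dosing who stays there is recovered at time zero. For the alleviation-or-improvement pair this holds only when every symptom is either new and mild or pre-existing and unworsened. Duration of fever and individual-symptom alleviation have the same gap for patients already afebrile or already at threshold.

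The size depends on f, which the documents do not give, and on the assumed exponential medians of 240 and 180 h. Over f = 10 to 40% the 60-hour difference in medians becomes 51 to 16 h, and from 50% both medians are zero. The optional Wilcoxon test loses more power than log-rank.

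A reader might go further and infer that time-zero recoveries will be frequent, or that the trial's main result is compromised. The documents support neither: they show only that all-mild entry is allowed, and the primary viral RNA analysis does not use the diary. This is an inexpensive improvement to secondary, descriptive endpoints.

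**What to change.** In SAP 5.4.2.3, analyse each symptom or fever time-to-event endpoint in the mITTi patients who do not already meet its criterion before dosing:
- **time to alleviation:** at least one of Items 1–12 scored 2 or 3 on the pre-dose Day 1 diary;
- **alleviation or improvement:** at least one of the three criteria unmet before dosing;
- **duration of fever:** pre-dose temperature above 37.5°C;
- **individual symptom:** that item above its own threshold before dosing.

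State that the qualifying period can start only after the first dose. Report by arm the number of patients already at response level for each endpoint, and keep the full mITTi analysis as supportive.

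The change is wording only. It uses data already collected, and because the sets are defined on pre-dose values the randomized comparison is kept. The cost is fewer patients in each symptom analysis, and results that apply only to patients above threshold at baseline.

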6.4 VIROLOGY AND EFFICACY ANALYSES

All virology and efficacy analyses will be performed on the mITTi population.

Sensitivity analyses to evaluate the robustness of results to the primary analysis methods (e.g., handling of dropouts) may be conducted and will be described in the SAP.

No alpha adjustments for multiple comparisons are planned.

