4. ANALYSIS SETS

Disposition summaries will be based on the intent-to-treat (ITT) population. All randomized patients will be included in the ITT population, and data will be summarized according to the randomized treatment assignment.

All primary and secondary virology and efficacy outcomes will be analyzed in the mITTi population. The mITTi population is defined as all patients randomized in the study who received any amount of study drug and had at least one positive SARS-CoV-2 RT-PCR test result above or equal to the limit of quantification (LOQ) during the study, with patients grouped according to the treatment assignment at randomization.

Safety analyses will be performed on the safety evaluable population, which consists of all patients who receive any amount of study drug. In all safety analyses, patients will be grouped according to the treatment that the patients actually received rather than the treatment assigned at randomization. Patients who received any dose of AT-527 will be summarized in the AT-527 group.

Pharmacokinetic analyses will be performed on the PK analysis population, which will consist of all patients in the ITT population who had at least one post-dose drug concentration measurement at a scheduled visit timepoint.

The analysis populations are defined in [Table 2](#).

Table 2 Analysis Sets

Population	Definition
ITT	All randomized patients, whether or not the patient received the assigned treatment.
Safety-evaluable	All patients who received at least one dose of study treatment.
mITTi	All patients randomized in the study that received any amount of study drug and had at least one positive central SARS-CoV-2 RT-PCR test result above or equal to the LOQ (by nasopharyngeal swab) during the study, with patients grouped according to the treatment assignment at randomization
PK population	All patients in the ITT population who had at least one post-dose drug concentration measurement at a scheduled visit timepoint

ITT=intent-to-treat; mITTi=modified intent-to-treat infected; LOQ=limit of quantification; PK=pharmacokinetic; RT-PCR=reverse-transcription polymerase chain reaction; SARS-CoV-2= severe acute respiratory syndrome coronavirus-2.

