6. SUPPORTING DOCUMENTATION

Appendix 1 Changes to Protocol-Planned Analyses

This section is not applicable, since there are no changes to protocol-planned analyses.

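### The individual-symptom and fever endpoints in SAP 5.4.2.3 have no at-risk condition, so patients who already meet the criterion before dosing count as very early events and pull the reported median towards its floor

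*SAP*

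**What the plan says.** **Endpoints (SAP 5.4.2.3).** For an individual symptom the criterion is "Score of 0 or 1 for Items 1–12 of the COVID-19 Symptom Diary", or a score of 0 on Items 13 and 14, held for at least 21.5 hours. For fever, "Duration of fever is defined as the time from start of treatment to return to an afebrile state", meaning 37.5°C or below held for at least 21.5 hours. For both, "the time at which the endpoint is met is the time of the start of the period when the criterion is met". Protocol 6.4.2.2 gives matching definitions.

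**Population.** The efficacy time-to-event endpoints are described through Day 28 "between the AT-527 group and the combined placebo group from all available cohorts using the mITTi population". SAP Table 2 defines mITTi as randomised, dosed patients who "had at least one positive central SARS-CoV-2 RT-PCR test result above or equal to the LOQ (by nasopharyngeal swab) during the study". Protocol 6.4 agrees: "All virology and efficacy analyses will be performed on the mITTi population". Protocol 4.1.1 requires symptoms consistent with mild or moderate COVID-19, but no particular symptom, minimum diary score or fever.

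**Timing.** The first diary, which also records temperature, is completed before the first dose (Protocol 4.5.7.2 and the footnotes to Appendices 1–3). Entries are then twice daily to Day 14.

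**Outputs.** The median with an 80% CI is to be presented, with Kaplan-Meier plots where appropriate. Also, "A summary of the symptom severity for each symptom in the COVID-19 symptom diary will be provided at baseline, Day 14 and Day 28". SAP 5.4.2.2 adds temperature summary statistics and a plot of mean temperature to Day 28.

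**Handling rules.** SAP Table 9 has rows for death, discontinuation or loss to follow-up, and endpoint not met. It has none for a criterion already met before dosing. The sensitivity analyses in SAP 5.4.2.5 do not cover it either.

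**The concern.** A time-to-alleviation endpoint describes patients who have something to recover from. Here the analysis set is defined by virology, and the event can be dated to a period that begins before treatment. A patient with no diarrhoea, or with a mild cough, can therefore enter the analysis as an immediate success.

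The reported median then mixes two quantities: how fast affected patients recover, and how many patients were already at or below the threshold. If the second share is large, both arms report medians near zero and the difference disappears even if the drug works. A reader who took those medians at face value would see no effect.

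The SAP also leaves open whether a qualifying period that began pre-dose is dated to time 0 or to the first post-dose diary. Programmers following the same text could produce different results.

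**Working it through.** The plan states no median, event count or power for these endpoints, so there is no figure to reproduce.

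**1. The rule applied to example diaries** (pre-dose, then every 12 hours; Items 1–12; qualifying period at least 21.5 hours):

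| Diary pattern | Pre-dose entry can start the period | Only post-dose entries count |
|---|---|---|
| Score 0 throughout | event at 0 h | event at 12 h |
| Score 1 (mild) throughout | event at 0 h | event at 12 h |
| Score 0 to 24 h, moderate 36–84 h, then 0 | event at 0 h | event at 96 h |
| Score 0 pre-dose, moderate 12–60 h, then 0 | event at 72 h | event at 72 h |

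The first two rows are the core of the problem. The third shows that the unstated dating rule can move one patient by four days. The fourth shows that a patient who worsens within the first 21.5 hours is not an early event.

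**2. Effect on the median.** Let s be the share of an arm that meets the criterion pre-dose and holds it. Date these patients to time 0, and let the others have exponential times with median m. The overall median solves (1 − s)·2^(−t/m) = 0.5, so

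t = m·[1 + log2(1 − s)] for s < 0.5, and t = 0 for s of 0.5 or more.

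With equal s in both arms the between-arm difference shrinks by the same factor. The medians of 72 h and 96 h are assumed for illustration:

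| s | Fraction kept | Medians reported | Difference (true 24 h) |
|---|---|---|---|
| 20% | 1 + log2(0.8) = 0.68 | 48.8 vs 65.1 h | 16.3 h |
| 30% | 1 + log2(0.7) = 0.49 | 35.0 vs 46.6 h | 11.7 h |
| 40% | 1 + log2(0.6) = 0.26 | 18.9 vs 25.3 h | 6.3 h |
| 50% or more | 0 | 0 vs 0 h | 0 h |

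For Weibull times with shape k the fraction is raised to the power 1/k. Over k = 0.8 to 2 it is 62–82%, 41–70% and 19–51% at s = 20%, 30% and 40%. Once more than half of an arm qualifies, the median is at its floor for any distribution.

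**3. Sample sizes.** Cohort A has 30 active patients, or 27 in mITTi at the assumed 90% positive rate. The SAP's pooled placebo is 30 + 4 × 10 = 70, about 63 in mITTi. Protocol Cohorts A–D give 30 + 3 × 10 = 60, about 54. The number at the floor is binomial. For 27 vs 63 (both odd, so half an arm is never an exact tie), the chance that both medians are at the floor is 0.8%, 25% and 81% at s = 40%, 50% and 60%. The chance that at least one is: 19%, 75% and 99%.

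**4. Dating rule and remedy.** Simulation with 27 vs 63, exponential times, assumed true medians of 4 days (active) and 6 days (placebo), and half-day diaries:

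| s | Mean difference, dated to time 0 | Dated to 0.5 day |
|---|---|---|
| 20% | 1.3 days | 1.3 days |
| 40% | 0.5 days | 0.4 days |
| 50% | about 0 | about 0 |

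The dating choice moves the floor but does not restore the contrast. Restricting to at-risk patients gives about 2.0 days at s = 40%. At that s, the difference is zero or negative in about 44% of trials using all mITTi and 18% using the subset.

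**The case against.** **Wording.** Alleviation and return to an afebrile state presuppose a symptom or a fever. For fever this is a fair reading, and it makes that half of the point weaker. It is still not an analysis rule. For Items 1–12 the wording helps less, because a patient with a mild symptom has the symptom and already satisfies the criterion.

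**Other displays.** If early events are dated together, the first step of a Kaplan-Meier curve shows their share, and later separation remains visible. The baseline severity summary, which includes the feverish item, and the mean temperature plot add context. A reader might infer that the problem would go unseen, and the documents do not support that. These displays do not, however, correct the median and its 80% CI.

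**Importance.** The endpoints are secondary and descriptive, formal tests are optional (SAP 5.4.1), and the study is described as hypothesis-generating. All of this stands and limits the weight of the point.

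**Scope.** The composite endpoints requiring a score of 0 or 1 on all of Items 1–12 also lack a baseline condition. To be an early event there, a patient must be at or below mild on every item. A count of such patients is therefore a reasonable first step.

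**Conclusion.** The gap is real and worth closing. As written, the plan turns patients who already meet the criterion into events at or near time zero, and the planned median understates time to alleviation among those with something to alleviate. The case is strongest for the individual symptoms.

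The size is conditional. It rests on s, which the documents do not give, and below 50% on the assumed shape of the recovery times and on equal s in both arms. Only the floor beyond half an arm is free of distributional assumptions.

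Three stronger readings should be resisted:
- That these medians will be at the floor, or a real effect hidden. Nothing in the documents fixes s for any item.
- That all early events are patients without the symptom. On Items 1–12, those with a mild symptom count too.
- That the trial's main conclusion is at risk. The primary RNA analysis does not use these endpoints.

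**What to change.** In SAP 5.4.2.3, for the individual-symptom and fever endpoints:

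1. Make the main analysis the mITTi patients who do not meet the criterion at the pre-dose Day 1 diary: score 2 or more on Items 1–12, the impaired response on Items 13–14, temperature above 37.5°C.
2. Report per arm the number not at risk (splitting score 0 from score 1 on Items 1–12), how many of those later cross the threshold, and the number with no pre-dose entry.
3. Keep the all-mITTi version as supplementary, with a stated rule for dating a period that begins pre-dose.
4. For the composite score 0 or 1 endpoints, report the number already meeting the criterion pre-dose.
5. Record the change in SAP Appendix 1, which now reads "This section is not applicable, since there are no changes to protocol-planned analyses", because Protocol 6.4 assigns all efficacy analyses to mITTi.

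**Cost.** No new data are needed. Denominators shrink and differ by endpoint. If 40% already meet the criterion pre-dose, they are at most about 27 × 0.6 = 16 active against 54 × 0.6 = 32 to 63 × 0.6 = 38 placebo, and fewer with missing pre-dose entries. Rare symptoms may support counts only, and symptoms that begin after baseline appear as counts. Treating baseline-mild patients as not at risk is a choice, which is why the split is requested. The subset is fixed before dosing, so it adds no post-treatment selection beyond that already in mITTi. The comparison with placebo pooled over sequential cohorts remains partly non-concurrent.
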